#### **8.4.3.5 Complete Population Analysis**

The primary efficacy analysis and key secondary analyses will be repeated in subjects who have non-missing/non-imputed data for the run-in period and the double-blind period. The analyses to be repeated are:

- Number of migraine days: comparison of treatment groups
- Responder rate as measured by percentage reduction in migraine days
- Number of headache days: comparison of treatment groups
- Number of days with acute headache medication: comparison of treatment groups

#### **8.4.3.6 Pooling Analyses**

Poolability of study sites will be assessed by comparing change in migraine days= trt\*site interaction; if  $p < 0.10$ , results will be stratified by site. Sites with less than five (5) subjects enrolled will be combined into a pseudo-site for purposes of analysis. To protect against having an overly large pseudo-site, when one

pseudo-site exceeds ten subjects, a second pseudo-site will be formed. This process will continue as needed each time a pseudo-site exceeds ten subjects.

## **8.5 Safety Analyses**

### **8.5.1 Device Exposure and Compliance**

The number and percentage of subjects administering at least 1 stimulation for each time period during the randomized period, and separately during the open-label period will be summarized by device group.

Compliance with device usage will be summarized descriptively by device group for each time period.

### **8.5.2 Adverse Events/Adverse Device Effects**

Analysis of AE/ADEs will be carried out on the safety population. All AE/ADEs will be included in the analyses, summaries, and individual subject data listings.

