**Table 2. Clinical Investigation Flow Chart**

Period	Run-in	Randomized					Open label					
Visit number	V1	V2	V3*	V4	V5 **	V6	V7 *	V8	V9**	V10	V11	V12
Week	-4	0	1	4	8	12	13	16	20	24	30	36
Day	-28	1+/-3	7+/-3	28+/-3	56 +/- 5	84 +/-5	91 +/-3	112 +/- 3	140+/-5	168+/-5	210 +/-5	252+/-5
Signed Consent Form	✓											
Randomization		✓										
Demographics	✓											
Inclusion/Exclusion criteria	✓											
History of migraine	✓											
Medical and surgical history	✓											
Physical examination	✓											
ECG	✓											
Urine pregnancy test 	✓											
Blood pressure and weight	✓					✓						✓
HIT-6 		✓		✓	✓	✓	✓	✓	✓	✓		✓
EQ-5D-5L 		✓		✓	✓	✓	✓	✓	✓	✓		✓
MIDAS 		✓				✓				✓		✓
Subject satisfaction question						✓						✓
Easy to use question						✓						✓
Blinding question			✓			✓						
Device training and placement		✓		✓		✓						
Collect device/ gammaCore®-R						✓						✓
Diary completion	✓	✓	✓	✓	✓	✓	✓	✓	✓	✓	✓	✓
Concomitant medication	✓	✓	✓	✓	✓	✓	✓	✓	✓	✓	✓	✓
Adverse Event 		✓	✓	✓	✓	✓	✓	✓	✓	✓	✓	✓
Study Termination												✓

 Fertile woman only.

 All new events during the run-in will be reported under adverse events.

Call\* - One week after the previous visit.

Call \*\*- One month after the previous visit.

 At visit 2 and 6 these questionnaires will be completed by the subjects on paper forms during the visit.

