### 5.3 Safety Population

The safety set will consist of all subjects who sign informed consent and are thus enrolled. The Safety population will be analyzed based on actual treatment received.

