### 7.5.2 Adverse Events

Adverse events will be collected and coded using the current version of the Medical Dictionary for Regulatory Activities (MedDRA v18.1).

An adverse event is considered treatment-emergent if the date of onset is on or after the date of first stimulation in the randomized period, or worsened during the randomized or open-label periods (intensity and/or severity changed to a worse grade).

**Events with Irregular Start Dates:** All adverse events will be included in the tabulations regardless the completeness of the onset dates. Partial dates may be imputed when appropriate.

If a partial date is reported for the start of an adverse event, a complete date will be estimated by the following algorithm in order to determine treatment emergent:

1. If month and day are missing: The year of the event will be compared to the year in which study treatment began. If the two years are not the same, then January 1 will be used. If the two years are the same, then the earlier of the date of randomization and the date of first usage of the device will be used.
2. If day is missing: The month and year of the event will be compared to the date in which study treatment began. The onset date will be imputed as the date closest to (being either on or after) the earlier of the date of randomization and the first date of usage of the device. If the two did not occur in the same month and year, then 1 will be used for the day.

If a partial date is reported for the end of an adverse event and the adverse event is not continuing, a complete date will be estimated by the following algorithm:

1. If month and day are missing: The year of the event will be compared to the year of final contact with the subject. If the two years are not the same, then December 31 will be used. If the two years are the same, then the date of final contact with the subject will be used.
2. If day is missing: The year of the event will be compared to the year of final subject contact. If the two years are not the same, then the last day of the month will be used for the day. If the two years are the same, then the month of the event will be compared to the month of final subject contact. If the months are not the same, then the last day of the month will be used for the day. If the two months are the same, then the date of final subject contact will be used.

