#### **AE/ADE Counting Rules:**

- A subject with more than one different adverse event in a particular system organ class (SOC) will be counted only once in the total of subjects experiencing adverse events in that particular SOC.
- A subject having experienced the same event (AE preferred term) more than once during the study will be counted only once in the number of subjects with that event.
- If an event changes in intensity or in seriousness during the study, a subject will be counted only once with the worst grade and seriousness respectively.
- If the causal relationship to the study device is assessed differently, a subject will be counted only once by considering the “Worst” documented degree of relationship.

Frequency and percentage of subjects experiencing a specific adverse event will be tabulated by system organ class, preferred term, and treatment group for each study phase (i.e., double-blind randomized period, open-label period). Summary tables and subject data listings will be provided for adverse events by maximum intensity, device-related adverse events, serious adverse events, adverse events causing discontinuation of the device or participation in the study, and deaths.

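### SAP 8.5.2 never applies the treatment-emergent definition of 7.5.2, and it gives no study phase or device attribution for the intensity, device-related, serious, discontinuation and death tables

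*SAP*

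**What the plan says.** Section 7.5.2 gives the definition: "An adverse event is considered treatment-emergent if the date of onset is on or after the date of first stimulation in the randomized period", or if the event worsened in the randomized or open-label period. It adds rules for incomplete start dates, under which "a complete date will be estimated by the following algorithm in order to determine treatment emergent".

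Section 8.5.2 works on the safety population and states: "All AE/ADEs will be included in the analyses, summaries, and individual subject data listings". The term treatment-emergent does not occur anywhere in section 8.5.

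Footnote 2 of Table 2 reads: "All new events during the run-in will be reported under adverse events". Section 3.1 says that no investigational treatment is given in the run-in. Under section 5.3 the safety set is everyone who consented, and "The Safety population will be analyzed based on actual treatment received".

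The counting rules in 8.5.2 count a subject once per preferred term over the study, at the worst intensity, seriousness and relationship. The system organ class and preferred term table is then given by "treatment group for each study phase (i.e., double-blind randomized period, open-label period"). The next sentence names the other tables without a phase: "Summary tables and subject data listings will be provided for adverse events by maximum intensity, device-related adverse events, serious adverse events", then events leading to discontinuation, and deaths.

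Section 3.1 moves sham subjects to the active device for the 24-week open-label period. Section 8.1 makes treatment group the default column for categorical summaries.

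**The concern.** There are two gaps, and they compound each other.

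First, the SAP builds a classification and a date algorithm to separate events that arise on a device from those that do not. It then tells the programmer to summarize everything. Events from four weeks without any device are therefore in scope for the summary tables.

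Second, five tables that carry the harms of most interest have no stated phase, while roughly half of the subjects change device partway through. The rule on treatment received gives no single answer for someone who received sham for 12 weeks and active for 24. Two programmers could put the same open-label serious event in different columns, and both could claim to follow the SAP.

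At stake is the randomized, sham-controlled comparison of serious, severe and device-related events. Efficacy is not affected.

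**Working it through.** The SAP states no figure on this point, so there is none to reproduce. The check sets the sections side by side, derives exposure shares from the design, and then illustrates the effect with assumed rates.

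**1. Which events and phases each table covers**

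| Output in 8.5.2 | Phase stated | Treatment-emergent only |
|---|---|---|
| System organ class / preferred term | Double-blind, open-label | Not stated |
| Maximum intensity | None | Not stated |
| Device-related | None | Not stated |
| Serious | None | Not stated |
| Discontinuation | None | Not stated |
| Deaths | None | Not stated |

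Run-in is not among the phases of the first table, which sits badly with the statement that all events enter the summaries. For the other five, the all-events statement and whole-study counting are the only scope rules given. Consented subjects who were never randomized belong to the safety set but have no defined column.

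**2. Exposure of a sham-randomized completer (section 3.1)**

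- Run-in 4 weeks, sham 12 weeks, active 24 weeks; total 40.
- Share of device time on active: 24/(12 + 24) = 67%.
- Share of all follow-up on sham: 12/40 = 30%; on active: 24/40 = 60%; before any device: 4/40 = 10%.

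**3. Illustration (assumed rates, not from the SAP)**

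Assume constant hazards, full completion, and a first-event risk per 12 weeks of 10% on active and 5% on sham.

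- Double-blind phase only: 0.10/0.05 = 2.0.
- Weeks 0 to 36 by randomized group: active 1 − 0.9³ = 0.271; sham 1 − 0.95 × 0.9² = 0.2305; ratio 0.271/0.2305 = 1.18.

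Other assumed weekly hazards, with risk = 1 − exp(−hazard × weeks). Over the whole study the active arm has 36 weeks at the active hazard; the sham arm has 12 weeks at the sham hazard plus 24 at the active hazard:

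| Weekly hazard, active / sham | Double-blind risks | Ratio | Whole-study risks | Ratio |
|---|---|---|---|---|
| 0.01 / 0.005 | 11.3% / 5.8% | 1.94 | 30.2% / 25.9% | 1.17 |
| 0.02 / 0.005 | 21.3% / 5.8% | 3.66 | 51.3% / 41.7% | 1.23 |
| 0.02 / 0.01 | 21.3% / 11.3% | 1.89 | 51.3% / 45.1% | 1.14 |

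Adding four run-in weeks at the sham hazard changes the first whole-study ratio only from 1.17 to 1.15. On these assumptions the change of device does most of the diluting and the run-in events little.

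**4. The alternative column rule**

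Suppose instead that phases are pooled and open-label events of former sham subjects go to the active column, with those subjects counted in both columns. Under the rates at the start of step 3 and 1:1 allocation, the active column is the average of 0.271 (36 weeks) and 1 − 0.9² = 0.19 (24 weeks), which is 0.2305. The sham column stays at 0.05 over 12 weeks. The ratio is 0.2305/0.05 = 4.6, inflated because exposure times differ. Depending on the layout, the same data would show 1.18, 2.0 or 4.6.

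**The case against.** The strongest reply is that this is silence, not a specification of pooling. Where 8.5.2 names treatment group it names phase in the same phrase, and the five tables are subsets of the same events, so a programmer could naturally carry the split forward. The sentence listing those tables names neither phase nor group; group columns come only from the general default in 8.1. Section 1 describes the SAP as general guidelines. In addition, device-related events should not arise in a device-free run-in, the all-events statement also covers listings, where run-in events belong, and the risk ratios rest on invented hazards.

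Much of this stands. The preferred term table is already split by group and phase, so former sham subjects' events are not mixed there. Carrying the split forward is a sensible reading, and under it no dilution occurs. The device-related table should hold no run-in events.

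The reply does not close the gap. Nothing requires the split for the five tables, and counting once over the study points the other way. The definition and date algorithm in 7.5.2 remain without a use in 8.5.2.

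A reader might infer more: that the SAP places former sham subjects' active-device events under sham, or that the extended-safety aim is not met. The documents do not support either. Filing those events under sham is one reading, and it fits poorly with analysis by treatment received. Open-label safety is covered by the preferred term table, the open-label device-use summaries in 8.5.1 and the listings.

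**Conclusion.** The point holds as an internal inconsistency and an undetermined layout. The treatment-emergent definition is not applied in 8.5.2. The five tables have no phase, and no rule places a subject who used both devices. These are facts of the text.

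The size is conditional. The 67% share of device time on active follows from the design for a sham-randomized completer. The fall from 2.0 to about 1.18 requires pooled phases, columns by randomized group, constant hazards, full completion and the assumed 10% and 5% risks. It shows direction and possible scale and does not predict this trial's result. If active carries the higher hazard, that layout pulls the ratio towards 1 at every set of rates tried. The change is worth making before unblinding, because otherwise the layout of the serious-event table could be chosen with the data in view.

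**What to change.** In section 8.5.2:

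- Base the AE summary tables on treatment-emergent events as defined in 7.5.2, and present run-in events in a separate listing.
- Extend the phase split already used for the preferred term table to the maximum-intensity, device-related, serious, discontinuation and death tables.
- Apply the count-once and worst-grade rules within each phase.
- Assign each event to the device in use at its onset or worsening, and use the subjects who entered that phase as the denominator.

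A pooled column for all active-device exposure, with events per subject-month because the phases last 12 and 24 weeks, would be useful but is optional.

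The cost is a few sentences in the SAP and some additional table columns. All the data needed are already collected.

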#### **AE/ADE Counting Rules:**

- A subject with more than one different adverse event in a particular system organ class (SOC) will be counted only once in the total of subjects experiencing adverse events in that particular SOC.
- A subject having experienced the same event (AE preferred term) more than once during the study will be counted only once in the number of subjects with that event.
- If an event changes in intensity or in seriousness during the study, a subject will be counted only once with the worst grade and seriousness respectively.
- If the causal relationship to the study device is assessed differently, a subject will be counted only once by considering the “Worst” documented degree of relationship.

Frequency and percentage of subjects experiencing a specific adverse event will be tabulated by system organ class, preferred term, and treatment group for each study phase (i.e., double-blind randomized period, open-label period). Summary tables and subject data listings will be provided for adverse events by maximum intensity, device-related adverse events, serious adverse events, adverse events causing discontinuation of the device or participation in the study, and deaths.

### **8.5.3 Concomitant Medications/Treatments**

A listing of concomitant treatments and medications will be generated.

### **8.5.4 Vital Signs**

Vital signs (blood pressure, pulse, height, weight and BMI) will be summarized using the number of non-missing observations, mean, median, standard deviation, minimum, and maximum. Summaries will be produced by device group for each assessment time.

### **8.5.5 Electrocardiogram**

A listing of ECG results will be generated.

### **8.5.6 Physical Examination**

The number and percentage of subjects with abnormal findings on the physical examination will be summarized for each device group by physical examination system.

### **8.6 Exploratory Analyses**

Additional, ad hoc exploratory analyses may also be conducted.

## **9. STATISTICAL SOFTWARE**

All tables, listings and figures will be primarily produced using SAS Version 9.3 (SAS Institute, Cary, NC) or a later version of SAS and R.

## **Appendix 1: Sensitivity Analyses: Multiple Imputation and Control-based Pattern Mixture Model**

Multiple imputation will be used to impute missing data. First, any non-monotone missing data patterns will be made monotone by imputing the intermittent missing data using the Monte Carlo Markov Chain (MCMC) approach. This imputation will be performed 100 times, resulting in a dataset with 100 copies of monotone data. If no non-monotone missing data patterns exist, this step is not necessary. Missing data will then be imputed using the monotone regression method. The following factors/covariates will be included in the model: treatment, center and number of migraines in the 4-week run-in period.

The data will be analyzed by t-test and ANCOVA, for each of the 100 imputations, and the results combined using standard multiple imputation methodology to obtain the appropriate estimates of variability.

The control-based pattern mixture model is a sensitivity analyses which addresses the possibility that the missing data is missing not at random (MNAR). The sham group will act as the control; and, the observed data from this group will be used to impute the missing data in both the sham and active groups.

The method is designed to impute data from monotone missing data patterns, thus the patterns of missing data are first examined and described. Any non-monotone missing data patterns will be made monotone first by imputing the intermittent missing data using the Monte Carlo Markov Chain (MCMC) approach. This imputation will be performed 100 times, resulting in a dataset with 100 copies of monotone data. If no non-monotone missing data patterns exist, this step is not necessary.

To implement the control-based pattern mixture model, the missing endpoint assessment for treatment and sham subjects is then imputed based on a linear regression model using observed data in the sham group, with the missing assessment as the dependent variable. The following factors/covariates will also be included in the model: treatment, center and number of migraines in the 4-week run-in period.

The data will be analyzed by t-test and ANCOVA, for each of the 100 imputations, and the results combined using standard multiple imputation methodology to obtain the appropriate estimates of variability.

An example of SAS code that may be used to implement the MCMC intermittent missing data imputation is:

```
proc mi data=indsn out=outmono n impute=100 seed=startseed ;
  class trt center;
  var trt center base depvar;
  mcmc chain=multiple impute=monotone;
run;
```

An example of SAS code that may be used to implement the control-based PMM is:

```
proc mi data=missdsn out=outdsn n impute=100 seed=startseed2 ;
```

```
class trt center;
var center base depvar;
monotone reg(/details);
mnar model(depvar / modelobs=(trt="sham"));
run;
```

## Appendix 2: Bang Blinding Index

To assess the blinding, the Bang blinding index and corresponding confidence interval will be estimated as follows. A 2x3 table will be constructed as shown:

Assignment	Guess			Total
	Active	Sham	Do not Know (DK)	
Active	$n_{11}(p_{1 1})$	$n_{12}(p_{2 1})$	$n_{13}(p_{3 1})$	$n_{1.}$
Sham	$n_{21}(p_{1 2})$	$n_{22}(p_{2 2})$	$n_{23}(p_{3 2})$	$n_{2.}$
Total	$n_{.1}$	$n_{.2}$	$n_{.3}$	$N$

Where  $p_{j|i} = P(\text{guess } j|\text{assignment } i)$  for  $i = 1(\text{Active}), 2(\text{Sham})$ , and  $j = 1(\text{Active}), 2(\text{Sham}), 3(\text{DK})$ , where DK denotes Don't Know. N is the total number of respondents.

If data is constructed in a 2x3 format as shown in the above table, let us define

$$r_{j|i} = p_{j|i}/(p_{1|i} + p_{2|i})$$

which is the proportion of correct guesses among participants who provided certain guesses other than DK in the  $i$ -th arm. Bang's BI is defined as  $(2 r_{j|i} - 1) * (p_{1|i} + p_{2|i})$  and can be estimated by:

$$\text{Bang's BI} = (2n_{ii}/(n_{i1} + n_{i2}) - 1) * ((n_{i1} + n_{i2})/(n_{i1} + n_{i2} + n_{i3}))$$

And its variance is given by

$$\text{Var}(\text{Bang's BI}) = (p_{1|i}(1 - p_{1|i}) + p_{2|i}(1 - p_{2|i}) + 2p_{1|i}p_{2|i})/n_i$$

Bang's BI is between -1 and +1 inclusive and can be interpreted as the proportion of participants who answered correctly on the  $i$ th arm beyond chance level.

A rule of thumb explanation on how to interpret Bang's BI is provided as follows:

- If  $r_{j|i}=1$  and  $n_{i3}=0$  (means all responses are correct), then  $\text{BI}_i=1$  (complete unblinding)
- If  $r_{j|i}=0$  and  $n_{i3}=0$  (means all responses are incorrect), then  $\text{BI}_i=-1$  (opposite guessing)
- If  $r_{j|i}=0.5$  (means 50% responses are correct), then  $\text{BI}_i=0$  (random guessing)

So, it is desired to show  $\text{BI}_i$  around 0. To test successful blinding, the null and alternative hypotheses can be constructed as follows:

$H_0$ : unsuccessful blinding vs  $H_1$ : successful blinding
